12.4 Reporting SUSARs

Any SAE that are suspected to be causally related to vaccination and are unexpected will be defined as SUSARs and will require expedited reporting to the DSMB, Sponsor, IRB/IEC and regulatory authorities which have approved the clinical trial and other organisations as required under the terms of the individual contracts (e.g. relevant pharmaceutical companies).

A detailed description of DSMB functions and responsibilities and guidelines on the transmission flow of SAEs /SUSARs will be provided in the DSMB charter. Table 6 provides details on the person responsible of reporting and timelines.

Table 6: Safety assessments reporting responsibilities

Safety event	Reported to	Reported by	The form of the report	Timeline
All SAEs	PI (or designee)	Treating physician	SAE form	Within 24 hours of awareness of event.
	KEMRI Scientific and Ethics Review Unit	PI (or designee)	Annual AE/SAE summary report	Annually
	Kenya Pharmacy and Poisons Board	PI (or designee)	Annual AE/SAE summary report	Annually
	LSHTM Research Ethics Committee (Sponsor)	PI (or designee)	Annual AE/SAE summary report	Annually
All life threatening SAEs and/or those suspected to be causally related to the vaccine	KEMRI Scientific and Ethics Review Unit	PI (or designee)	SAE form	Within one working day of notification of the event.
	Kenya Pharmacy and Poisons Board	PI (or designee)	SAE form	Within one working day of notification of the event.
	LSHTM Research Ethics Committee (Sponsor)	PI (or designee)	SAE form	Within one working day of notification of the event.
	DSMB	PI/ Sponsor (or designee)	SAE form	Within one working day of notification of the event.
	Pfizer Inc.	PI/ Sponsor (or designee)	SAE form	Within the delay established by their procedures
	GlaxoSmithKline plc.	PI/ Sponsor (or designee)	SAE form	Within the delay established by their procedures

12.5 Emergency Procedures

During vaccination, staff trained in basic life support will be available in case of adverse reactions around vaccination. An emergency kit will also be available and checked at each vaccination visit.

There will be no mandated pauses of vaccination triggered by SAEs unless the investigators, sponsors, or DSMB express concern.

12.6 Procedures for reporting any protocol violation(s)

Protocol violations will be reported to the sponsor and IRB/IEC and regulatory authorities as specified in their guidelines.

13 STATISTICAL ANALYSES

13.1 Primary analyses and Sample size

The primary endpoint of non-inferiority will be reached if the lower CI around the ratio of geometric mean concentration (GMC) of IgG (fractional/full dose) is ≥ 0.5 (i.e. the 2-fold criterion) at 1-month post-boost dose (10 months of age).

A secondary endpoint will assess the proportion of ‘responders’, defined as those with serotype-specific IgG antibody concentration ≥ 0.35 mcg/ml[13] at 4 weeks after the primary series (18 weeks of age). Non-inferiority will be achieved if the lower limit of the 95% confidence interval (CI) around the difference in the proportion of ‘responders’ (fractional dose group – full dose group) is $> -10\%$ [76] post-primary series (18 weeks of age) for at least 8 of the 10 vaccine types in the PCV10 arms and at least 10 of the 13 vaccine types in the PCV13 arms. Assessments of non-inferiority will be made separately for each of the vaccine type serotypes. Our primary endpoint will be reached across all arms if non-inferior immunogenicity is achieved for the 10 serotypes in PCV10 as this is the standard of care in Kenya currently.

The required sample size for the trial was calculated in order to ensure good power to detect both the primary and secondary immunogenicity endpoints, this approach is recommended in trials where both primary and secondary endpoints are important to determine the success of the intervention[77]. The proportion of children achieving the correlate of protection (IgG ≥ 0.35 $\mu\text{g/ml}$) varies across PCV10/13 serotypes after the primary vaccination series and by schedule (range 63.5-98.4%)[33, 76, 78-80]. In a prior study of PCV7 in Kilifi, the average proportion of children reaching the threshold antibody concentration across serotypes at 18 weeks of age was 87%[33]. The average proportion reaching the threshold antibody concentration at 18 weeks of age after 2 primary doses, 2 months apart, in European[81], Israeli[17, 82] and South African children[24] was also approximately 87% across 10 serotypes but serotype specific responses ranged between 63-97%. On this basis, to detect non-inferior immunogenicity (% responders) to 10 of the 13 serotypes in the PCV13 arms or 8 of the 10 serotypes in the PCV10 arms at 18 weeks of age with 90% power, we would need to enrol 300 infants per arm to declare non-inferiority using a margin of 10%, accounting for serotype-specific response rates, multiple serotype-specific comparisons and 5% loss to follow up at 4 weeks after the booster dose. Additionally, this sample size would allow us to perform an analysis on *all* vaccine types with a 12% non-inferiority margin with 84% power.

The 10-12% non-inferiority margin has been determined considering the public health consequences of a commensurate loss of protection, assuming 87% of infants achieve protection with the full dose.

There will be >99% power to declare non-inferiority using the criterion that the lower limit of the 95% CI for the ratio of GMCs (fractional/full dose) is >0.5. Based on the IgG GMCs elicited post boost in South Africa, which ranged between 13 and 35 mcg/ml for the PCV7 serotypes[24], we hope to be able to estimate GMCs with precision +/- 2-4 mcg/ml.

There will therefore be four pairwise comparisons of each vaccine type serotype for the primary endpoint of non-inferiority (i.e. full dose vs 20% dose; and full dose vs. 40% dose for each vaccine).

A co-primary analysis, which has a precedent in PCV licensure analyses[83], will determine whether the immune responses elicited by the fractional doses (20% and 40% doses) are non-inferior to the lowest serotype-specific immune response elicited by the full dose PCV, 4-weeks after the primary series. In PCV13 licensure analyses, the immunogenicity of new PCV13 serotypes, not included in PCV7, were assessed in non-inferiority comparisons with the lowest response observed among the PCV7 serotypes in PCV7 recipients, the response to serotype 6B, for which there was existing evidence of both efficacy and programmatic effectiveness[83]. In adapting this approach to our study, non-inferiority will be achieved if the lower limit of the 95% confidence interval (CI) around the difference in the proportion of 'responders' (fractional dose serotype 'x' – full dose 6B) is >-10%.

The timing of the primary endpoint, at 4 weeks after the booster dose, aligns with the aim to assess the effectiveness of the whole three dose schedule (rather than partial vaccination with 1 or 2 doses). It will give an indication of protection in the second year of life, this is clinically relevant as it is thought that the enhanced protection in the second year of life, as a result of a booster dose, has an important impact on carriage and transmission in toddlers, which may enhance herd protection, compared to a 3p+0 schedule[20]. In a 2p+1 schedule in Kenya, a smaller proportion of children may reach the protective threshold of antibodies after the 2 primary doses in early infancy, compared to after three primary doses, but in the context of low rates of disease after 6 years of PCV10 implementation, young infants would be protected by the indirect protection afforded by the reduced transmission of pneumococci. The timing of the endpoint corresponds to previous literature analysing 2p+1 schedules and is in line with standard practice to analyse non-inferiority trials in the ATP population.

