
vaccine-types[25]. In the UK, 2.5 years after vaccination in a 2p+1 schedule, >75% of children had circulating IgG to 5 of the 7 PCV7 serotypes at concentrations >0.35 mcg/ml[26]. Protection from carriage has been demonstrated out to at least 4 years post-vaccination in some studies for at least some PCV7 serotypes[27]. Further data are needed on the duration of protection after a 2p+1 schedule in LMIC settings, both between the primary series and boost dose and after the booster into the 2nd year of life[16, 27].

Safe and immunogenic co-administration of PCV7/9/13 with routine childhood immunisations has been demonstrated for all antigens in the schedule, including Diphtheria-Tetanus- acellular Pertussis vaccine with or without Inactivated Polio Vaccine and hepatitis B vaccine components, Measles-Mumps-Rubella, Varicella, Haemophilus influenzae Type b (Hib) and meningococcal conjugate vaccines [28-32]. Immunological responses to PCV in Kenyan infants are high; over 90% of a cohort of children following the routine immunisation schedule of 3p+0 achieved the immune correlate of protection 4 weeks after the third dose for all PCV7 serotypes[33].

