9 TRIAL DESIGN

9.1 Overall Study Design

A phase IV individually-randomised controlled trial of full or fractional (20% or 40%) doses of PCV10/ PCV13, given as a 3-dose schedule to infants: 2 doses at 6 and 14 weeks of age and a booster dose at 9-12 months (the 2p+1 schedule) or 3 full doses at 6, 10 and 14 weeks of age (the 3p+0 schedule) (Figure 1.).

At 6-8 weeks of age, 300 infants will be enrolled at random into each of the seven trial arms and followed until 18 months of age. The seven trial arms:

- A. Full dose PCV13 vaccination in a 2p+1 schedule.** This arm will demonstrate immunogenicity and carriage endpoints for an alternative schedule to 3p+0 as recommended by WHO, in the Kenyan population.
- B. 40% fractional dose PCV13 vaccination in a 2p+1 schedule.**

C. 20% fractional dose PCV13 vaccination in a 2p+1 schedule.

[figure not shown]
D. Full dose PCV10 vaccination in a 2p+1 schedule. This arm will demonstrate immunogenicity and carriage endpoints for an alternative schedule to 3p+0 as recommended by WHO, in the Kenyan population.

E. 40% fractional dose PCV10 vaccination in a 2p+1 schedule.

F. 20% fractional dose PCV10 vaccination in a 2p+1 schedule.

G. Full dose PCV10 vaccination in a 3p+0 schedule. This arm would represent the current vaccine and schedule in the Kenyan routine immunisation programme and would act as an additional comparison arm.

Figure 1. Clinical trial flow

¹ Immunogenicity samples at 9 and 18 months of age will only be drawn from 150/300 participants in each arm.
RI = routine immunisation.

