PCV10 was introduced in the national EPI programme in Kenya in 2011 in a three-dose schedule at 6, 10 and 14 weeks of age, with no booster dose (the '3p+0' schedule). In Kilifi County, a catch-up campaign in under 5-year olds was completed. PCV10 is delivered concomitantly with DTP-HepB-Hib (pentavalent) vaccine and oral Polio vaccine[65]. In Kilifi, the median age at receipt of the first dose of PCV10 in 2013-2016 was 6.1-6.3 weeks (personal communication [name]). At 14 weeks of age, IPV is also administered. In an evaluation of the impact of the new vaccine introduction in 2013 it was estimated that *S. pneumoniae* vaccine-serotype carriage had been reduced from 34% to 13% in children under 5 years of age in Kilifi[4]. This had been further decreased to 7% in 2016 but may be higher in areas outside of Kilifi in which no catch-up campaigns were conducted. It is expected that the fractional doses will be effective in preventing the acquisition of vaccine-serotype (VT) carriage, but if they are not, this will be apparent within the trial as study infants will be exposed (by contact with older children) to the vaccine serotypes. Furthermore, the reduction in vaccine type carriage prevalence over time has been matched by a commensurate increase in carriage of non-vaccine serotypes, particularly those contained in PCV13 but not in PCV10 (3, 6A and 19A) which are now found in 22% of all children under 5 years (cross sectional survey in Kilifi 2016; unpublished observation).

Although Kenya currently delivers PCV in a 3p+0 schedule, there is increasing pressure for LMICs to switch to a 2p+1 schedule to take advantage of the hypothesised increased herd protection with a booster dose[20]. In preparation for a potential future change in schedule we have designed the study to deliver fractional doses in a 2p+1 schedule; however, we are also incorporating a single arm of 3p+0 to 'bridge' the findings to the existing schedule. PCV7, PCV9 and PCV13 can be delivered concomitantly with DTP-HepB-Hib (pentavalent vaccine) and other routine immunisations including measles with no effect on the immunological responses to any of the antigens [29, 32, 60, 61, 66, 67]. There is currently no routine vaccination visit at 11-15 months of age in Kenya; however, measles vaccine first dose (MCV1) is delivered to children at 9 months of age and measles second dose was

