The results from the multiplex opsono-phagocytic assay (MOPA) to all vaccine serotypes plus 6C will be used to compare IgG functionality after 3 full doses of PCV10 or PCV13 with that after 3 fractional doses of PCV10 or PCV13 at 1-month post boost. Antibody function will also be compared between products for comparable schedules. The correlation between IgG concentration and functional activity following a third dose of PCV delivered in a 2+1 schedule will be assessed. Exploratory analyses will derive a functional correlate of protection against carriage using the post booster MOPA titre and vaccine type carriage at 18 months of age for serotypes 19A and 6A.

To evaluate the safety of the fractional dose delivery we will describe:

- the proportion of infants in each trial arm experiencing specified local vaccination site reactions (e.g. redness, swelling) within the 30 minutes immediately after vaccination as observed by study personnel;
- the proportion experiencing local/systemic adverse reactions, e.g. injection site abscess, in the 7 days after vaccination, as reported by mother or the legal guardian who accompanied the infant to the vaccination session at a day 8 visit.

We do not expect to have the statistical power to determine a difference in the risks of injection site abscess between arms as the risk of injection site abscess is expected to be low. Pentavalent vaccine delivered in 10-dose vials in Kenya resulted in 128 abscesses per 100,000 injections[84]. If this baseline level of risk applies to the 3 immunisations given to 1200

children in the fractional dose groups we would expect to see no more than 5 abscesses throughout the whole study.

The sera of all participants in the seventh trial arm (Arm G) will be assayed for immunogenicity to 7 serotypes (the PCV7 vaccine types) at 4-weeks post-primary series only. The proportion of responders in Arm G at 4-weeks post-primary series will be compared to that of the PCV10/13 2p+1 arms at 4-weeks post-primary series. Non-inferiority will be achieved if the lower limit of the 95% confidence interval (CI) around the difference in the proportion of 'responders' (2p+1 - 3p+0) is $>-10\%$ [76]. Assuming the proportion of children reaching the threshold antibody concentration across serotypes at 18 weeks of age is on average 87%[33], with 300 per arm, we would have 85% power to declare non-inferiority using a margin of 10%, accounting for 7 serotype-specific comparisons.

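### The 2p+1 versus 3p+0 (arm G) responder comparison is powered on a single 87% rate that, by the protocol's own account of the source study, cannot be that study's 3p+0 rate

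*Combined protocol and SAP*

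**What the plan says.** Section 13.1 takes a planning rate from a previous Kilifi study of PCV7 (reference 33): "the average proportion of children reaching the threshold antibody concentration across serotypes at 18 weeks of age was 87" per cent. It names no schedule for that figure. It then gives about 87% after two primary doses two months apart, averaged over 10 serotypes, in European, Israeli and South African children, with single serotypes from 63% to 97%.

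Section 13.2 plans the comparison of the 2p+1 arms with arm G on the PCV7 serotypes at 18 weeks. Its only rate is the Kilifi one: "Assuming the proportion of children reaching the threshold antibody concentration across serotypes at 18 weeks of age is on average 87%[33"]. With 300 per arm, a 10-point margin and allowance for 7 serotype comparisons, it states 85% power. Section 9.1 defines arm G as "Full dose PCV10 vaccination in a 3p+0 schedule".

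Section 5 cites the same reference 33 for a different figure: "over 90% of a cohort of children following the routine immunisation schedule of 3p+0 achieved the immune correlate of protection", measured "4 weeks after the third dose for all PCV7 serotypes[33"]. Section 9.2 describes the routine programme as a "three-dose schedule at 6, 10 and 14 weeks of age", so four weeks after its third dose is 18 weeks of age.

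On two doses against three, the document points both ways. Section 13.1 allows that in Kenya "a smaller proportion of children may reach the protective threshold of antibodies after the 2 primary doses" than after three. Section 5 cites evidence that IgG concentrations after two doses two months apart match those after three monthly doses.

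**The concern.** Sections 5 and 13.1 draw on the same study, vaccine and age. If every serotype is above 90% on 3p+0, the average on 3p+0 cannot be 87%. Section 13.2 nevertheless applies 87% to a comparison in which one side is exactly that schedule, and gives no separate rate for the other side.

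Section 9.2 says that arm G is included to bridge the 2p+1 results to the schedule now in use. A true gap of 3 points between schedules would use 3 of the 10 margin points. The power would then be well below the stated 85%, and a missed margin for some serotypes would be hard to interpret if the plan had not shown that possibility beforehand.

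**Working it through.** **Can both figures describe 3p+0?** Section 5 can be read serotype by serotype, or as the share of infants above the threshold for all seven serotypes together. Either way each serotype exceeds 90%, so the average does too, and 87% is excluded for that cohort. The two figures can coexist if the 87% describes or includes another schedule. The title of reference 33 concerns vaccination soon after birth, which suggests that the study had one. As an illustration only: with two equal groups and 3p+0 at 90%, a pooled 87% needs the other group at 2 × 87 − 90 = 84%.

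**Formula.** Normal approximation for non-inferiority of two proportions:

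Power = Φ( (0.10 − (pG − pT)) / SE − z ), with SE = √[ (pG(1−pG) + pT(1−pT)) / n ].

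Here pG is arm G, pT is the 2p+1 arm and n = 300. The 95% CI rule gives z = 1.960; Bonferroni over 7 (one-sided 0.025/7) gives z = 2.690.

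**The plan's figure.** With 87% in both arms, SE = √(0.2262/300) = 0.02746 and 0.10/SE = 3.642.
- One serotype, 95% CI: Φ(1.682) = 95.4%.
- Bonferroni over 7: Φ(0.952) = 82.9% (Šidák 83.0%).
- All 7 passing, treated as independent: 0.954^7 = 71.8% at one-sided 0.025; 0.977^7 = 85.0% at one-sided 0.05.

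The plan does not state its multiplicity method. Equal rates of 87% give 83% to 85% by three of these routes. The exact 85.0% comes from one-sided 0.05, which is looser than the 95% CI rule in section 13.2.

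**Separate rates.** With pG = 0.90 and pT = 0.87, SE = √((0.0900 + 0.1131)/300) = 0.02602 and 0.07/SE = 2.690. Power is Φ(0.730) = 76.7% per serotype and Φ(0.000) = 50.0% with Bonferroni. The same formula gives:

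| Arm G | 2p+1 | Per serotype, 95% CI | Bonferroni over 7 |
|---|---|---|---|
| 87% | 87% | 95.4% | 82.9% |
| 90% | 90% | 98.3% | 91.8% |
| 90% | 87% | 76.7% | 50.0% |
| 92% | 87% | 51.8% | 24.6% |
| 95% | 87% | 13.7% | 3.4% |
| 95% | 92% | 93.6% | 78.6% |

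Section 13.1 allows 5% loss, giving n = 285; the 90%/87% row then becomes 74.6% and 47.3%. The 90% is the floor of the section 5 figure; the 92% and 95% rates are assumptions. The loss comes from the gap between schedules: raising both rates together increases power.

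**The case against.** Section 13.1 names no schedule for the 87%, and only reference 33 could show whether it is a misquotation or a different group. A reader might infer that the protocol contradicts itself outright. The documents do not prove that; they show only that the 87% is not the 3p+0 rate if section 5 is right. This objection stands, but a figure from another or a pooled schedule is still the wrong planning rate for arm G.

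A reader might also infer that the comparison is planned on an equality that the authors do not expect. Section 13.1 says only that fewer infants may reach the threshold after two doses, and section 5 cites equivalent concentrations. Equivalent concentrations need not mean equal proportions above a threshold, but the plan is mixed rather than clearly expecting a gap.

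The 3-point gap pairs unlike figures. The over-90% result is from Kilifi infants given PCV7; the two-dose 87% is from other populations and 10 serotypes, whereas arm G is compared on 7. Arm G receives PCV10. Section 6 cites some evidence of higher antibody responses in African children, so the Kilifi two-dose rate could exceed 87%. This stands: the gap is a scenario, not an estimate, and equal rates remain possible.

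**Conclusion.** The concern holds for the planning rate of one secondary comparison. The 85% in section 13.2 rests on equal 87% rates, and 87% cannot be the source study's 3p+0 rate if section 5 reports that study correctly. With arm G at 90% and 2p+1 at 87%, power is about 77% per serotype and about 50% with Bonferroni over 7. It is lower if arm G exceeds 90% while 2p+1 stays at 87%. Equal rates of 90% give about 98% and 92%. All figures assume 300 evaluable infants per arm and the normal approximation.

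Three stronger readings are tempting but not supported:
- That 77% is a ceiling. It is one only while 2p+1 is held at 87%.
- That the comparison should be expected to fail. At 90% against 87%, a single serotype is more likely than not to pass.
- That the trial's sample size is undermined. The primary GMC endpoint and the fractional versus full comparisons lie within 2p+1, and the responder calculation there has the separate two-dose 87% behind it.

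**What to change.** In section 13.1, name the group and schedule that the 87% from reference 33 describes, and reconcile it with the over-90% figure in section 5.

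In section 13.2, replace the single 85% with power under separate 3p+0 and 2p+1 rates. Show a range that covers equal rates and a gap of 3 points or more, and state the multiplicity method. Note that the two-dose 87% comes from other populations, so it is a scenario rather than a Kilifi estimate.

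The cost is a text change in two sections, with no extra infants and no change to procedures. The downside is a less favourable stated power for a secondary comparison.

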13.2 Secondary analyses

We will present the serotype-specific difference in proportions of children with evidence of vaccine serotype carriage by trial arm. In Kilifi, residual carriage of PCV10 serotypes under the routine immunisation schedule has been estimated in 2016 at 6%; assuming 300 per arm, we expect to estimate the combined prevalence of PCV10 serotypes in each arm with an accuracy of $\pm 2.7\%$. Carriage of the 3 additional PCV13 serotypes in children aged under 5

years in Kilifi in 2016 was 22%; assuming 300 per arm, we expect to estimate combined prevalence of PCV13 serotypes in each arm with an accuracy of $\pm 5.0\%$.

The indirect effect of the PCV10 programme, which has been implemented in Kenya for 6 years, has reduced the carriage prevalence of PCV10 serotypes in Kilifi to 6% among children <5 years; this limits the power to examine the direct effect of different doses of PCV13 on carriage of the serotypes contained in PCV10. However, the population impact of the PCV10 programme has also led to an increase in the carriage prevalence of the serotypes that are contained in PCV13 but not in PCV10 (3, 6A and 19A). We will use carriage of these serotypes in the PCV10 full dose arm as a control against which to test of the direct effect of the full and fractional doses of PCV13. The effectiveness of PCV13 against carriage of serotype 3 is limited^{22 67} so we will concentrate in this analysis on serotypes 6A and 19A; the combined carriage prevalence of these serotypes among children aged <5 years in Kilifi is 19%. Assuming this prevalence at 18 months of age among the children receiving full dose PCV10, 300 infants per arm would confer 92% power to detect a 50% reduction in carriage in any of the PCV13 arms (leading to a prevalence of 9.5%); and 78% power to detect a 40% reduction in any of the PCV13 arms (leading to a prevalence of 11%). These effect estimates would be in line with previous literature on the direct effect of PCV13 on carriage prevalence⁶⁴⁻⁶⁶. A total of 290-300 per arm at 18 months of age would confer just over 80% power to determine whether full and fractional dose arms exhibit non-inferior prevalence of PCV10 vaccine-type carriage using a non-inferiority margin of 5%.

The results from the multiplex opsono-phagocytic assay (MOPA) to all vaccine serotypes plus 6C will be used to compare IgG functionality after 3 full doses of PCV10 or PCV13 with that after 3 fractional doses of PCV10 or PCV13 at 1-month post boost. Antibody function will also be compared between products for comparable schedules. The correlation between IgG concentration and functional activity following a third dose of PCV delivered in a 2+1 schedule will be assessed. Exploratory analyses will derive a functional correlate of protection against carriage using the post booster MOPA titre and vaccine type carriage at 18 months of age for serotypes 19A and 6A.

To evaluate the safety of the fractional dose delivery we will describe:

- the proportion of infants in each trial arm experiencing specified local vaccination site reactions (e.g. redness, swelling) within the 30 minutes immediately after vaccination as observed by study personnel;
- the proportion experiencing local/systemic adverse reactions, e.g. injection site abscess, in the 7 days after vaccination, as reported by mother or the legal guardian who accompanied the infant to the vaccination session at a day 8 visit.

We do not expect to have the statistical power to determine a difference in the risks of injection site abscess between arms as the risk of injection site abscess is expected to be low. Pentavalent vaccine delivered in 10-dose vials in Kenya resulted in 128 abscesses per 100,000 injections[84]. If this baseline level of risk applies to the 3 immunisations given to 1200

children in the fractional dose groups we would expect to see no more than 5 abscesses throughout the whole study.

The sera of all participants in the seventh trial arm (Arm G) will be assayed for immunogenicity to 7 serotypes (the PCV7 vaccine types) at 4-weeks post-primary series only. The proportion of responders in Arm G at 4-weeks post-primary series will be compared to that of the PCV10/13 2p+1 arms at 4-weeks post-primary series. Non-inferiority will be achieved if the lower limit of the 95% confidence interval (CI) around the difference in the proportion of 'responders' (2p+1 - 3p+0) is $>-10\%$ [76]. Assuming the proportion of children reaching the threshold antibody concentration across serotypes at 18 weeks of age is on average 87%[33], with 300 per arm, we would have 85% power to declare non-inferiority using a margin of 10%, accounting for 7 serotype-specific comparisons.

IgG GMCs in a random selection of half the participants in trial arms A-F at 9 months of age (pre-boost) and at 18 months of age (9 months post-boost) will be used to 1) estimate the duration at which GMCs remain above the threshold for protection in the first 2 years of life after a 2p+1 schedule of full or fractional doses and 2) to monitor carriage acquisition rates.

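### Minor: the 78% power given for a 40% reduction in 6A/19A carriage belongs to a 42% reduction (19% to 11.0%); a 40% reduction (to 11.4%) has about 74%

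*Combined protocol and SAP*

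**What the plan says.** Section 13.2 (Secondary analyses) uses carriage of serotypes 6A and 19A, which are in PCV13 but not PCV10, to test the direct effect of full and fractional PCV13. The full-dose PCV10 arm is the control. The baseline is a local survey figure: "the combined carriage prevalence of these serotypes among children aged <5 years in Kilifi is 19"%. It is carried to the trial's time point: "Assuming this prevalence at 18 months of age among the children receiving full dose PCV10".

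Two power statements follow in the same sentence:

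- First scenario: "300 infants per arm would confer 92% power to detect a 50% reduction in carriage in any of the PCV13 arms", with the result given as "leading to a prevalence of 9.5"%.
- Second scenario: "and 78% power to detect a 40% reduction in any of the PCV13 arms (leading to a prevalence of 11"%).

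Section 8.3 lists this comparison among the secondary objectives, with its main analysis at 18 months of age. Section 13.1 makes clear that the trial was not sized on it: "The required sample size for the trial was calculated in order to ensure good power to detect both the primary and secondary immunogenicity endpoints".

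**The concern.** The second scenario describes one effect in two ways that disagree. Starting from 19%, a 40% reduction leaves 11.4%, while a prevalence of 11% means a reduction of about 42%. The first scenario is printed to one decimal and is exact (half of 19% is 9.5%).

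If 11% were only 11.4% printed without its decimal, the power beside it would still be the power for 11.4%, and nothing would be wrong. The question is therefore which prevalence went into the calculation. If it was 11.0%, the stated power is too high for the effect size named.

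Low carriage of the PCV10 serotypes limits what the trial can show on those types, so the plan relies on 6A/19A to show a direct effect of PCV13. The 40% scenario is the smaller of the two effects that section 13.2 treats as consistent with earlier studies. Anyone reading a null result would use this power figure to judge how readily a 40% reduction could have been missed.

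**Working it through.** **Inputs**

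- Control prevalence p1 = 0.19 (section 13.2).
- n = 300 per arm, equal allocation (sections 9.1 and 13.2).
- PCV13-arm prevalence p2 = 0.095 or 0.11 as printed; 0.6 × 0.19 = 0.114 for a true 40% reduction.
- Significance level: section 13.2 states none for this comparison. Two-sided 5% (z = 1.960) is assumed and tested below against the printed powers.

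**Effect sizes**

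- 0.5 × 19% = 9.5%, as printed.
- 0.6 × 19% = 11.4%, not 11%.
- 1 − 11/19 = 42.1%, not 40%.

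**Formula** (two proportions, pooled variance under the null)

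Power = Φ[(p1 − p2 − 1.960 × SE0) / SE1], where SE0 = √(2p̄(1 − p̄)/n), SE1 = √((p1(1 − p1) + p2(1 − p2))/n) and p̄ = (p1 + p2)/2.

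| p2 | Reduction | p̄ | SE0 | SE1 | Argument of Φ | Power | Printed |
|---|---|---|---|---|---|---|---|
| 0.095 | 50% | 0.1425 | 0.02854 | 0.02828 | 1.381 | 91.6% | 92% |
| 0.110 | 42.1% | 0.1500 | 0.02915 | 0.02897 | 0.789 | 78.5% | 78% |
| 0.114 | 40% | 0.1520 | 0.02931 | 0.02915 | 0.636 | 73.8% | 78% |

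The first two rows reproduce the plan's figures. The third row, the effect the plan names, does not. A one-sided 5% test gives 95.5%, 86.6% and 83.0% for the three rows and matches neither printed power, so the two-sided assumption is well supported.

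**Could another method give 78% for 11.4%?** At 300 per arm, two-sided 5%, 19% against 11.4%:

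| Method | Power |
|---|---|
| Unpooled variance | 74.1% |
| Arcsine | 74.3% |
| Exact enumeration of the chi-square test | 74.2% |
| Log risk ratio | 72.3% |
| Continuity-corrected normal approximation | 69.9% |

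None reaches 78%.

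**Could rounding of the inputs explain it?**

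- With the reduction held at 40%, control prevalences of 18.5% to 19.5% (the values that round to 19%) give 72.4% to 75.1%.
- With both prevalences at their upper rounding edges (19.49% and 11.49%), power is 77.4%, but that is a 41.0% reduction (1 − 11.49/19.49).

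**What would make the sentence true?** At 300 per arm, 78% power corresponds to a reduction of about 42% from 19%. For a true 40% reduction, 78% power needs either a control prevalence of about 20.7% or about 333 infants per arm.

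**The case against.** The strongest reply is that the 78% is correct for the prevalence printed beside it. A reader who takes 19% against 11% with 300 per arm recovers the stated power, so the only inexact item is the word describing the effect. This is a fair account of how the slip arose, and it makes relabelling the effect a legitimate repair. It does not remove the inconsistency, because the sentence offers the figure as the power for a 40% reduction.

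A second point is that the gap depends on a test and significance level that the section does not state, and that methods differ: the value for 11.4% runs from about 70% to 74%. That stands against quoting 73.8% as if it were fixed, so "about 74%" is the right precision. It does not help the stated figure, since every two-sided 5% method tried falls below 78% and the assumed test reproduces both printed powers.

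Third, the consequence is small. This is a secondary analysis, 300 per arm was fixed on other endpoints, and the plan sets no power target for this comparison that 78% would meet and 74% would miss. Applying an under-5 survey prevalence to children of 18 months brings uncertainty of similar size: a control prevalence of 20.7% instead of 19% would give 78%. All of this stands and is why the point is minor. That uncertainty does not make the sentence correct on the plan's own inputs.

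**Conclusion.** The concern holds, as a minor arithmetic error. The printed power matches the printed prevalence of 11.0%, a 42% reduction, and not the named 40% reduction. For 40% (19% to 11.4%) the power at 300 per arm is about 74%, some 4 points lower, so a true effect of that size would be missed about 26% of the time, not 22%. The likeliest cause is that 11.4% was rounded to 11% before the power was computed.

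This rests on a two-sided 5% test of two proportions with all 300 infants per arm contributing at 18 months, and on the plan's 19% holding at that age. The 92% figure for a 50% reduction, the sample size and all decision rules are unaffected.

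**What to change.** Correct the one sentence in section 13.2 in either of two ways:

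- keep the effect and change the rest: about 74% power to detect a 40% reduction (to 11.4%); or
- keep the power and change the effect: 78% power to detect a 42% reduction (to 11.0%).

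The cost is one sentence of text. Sample size, visits, specimens and analyses do not change.
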